3.7.1 Schedule of Assessments

3.7.1.1 Screening (-30 days to 1 day prior to Baseline)

Screening for eligibility is required for all subjects. The screening and baseline visits may be combined with the last visit from either Trials 156-08-271 or 156-13-210 with all required assessments from each visit performed only once. Therefore, in some cases, if a subject enrolls in this trial from a prior tolvaptan trial, the end of trial or last follow-up visit for that trial and the screening and baseline visit for this one may occur simultaneously. Required assessments for the screening visit are as follows:

1. Obtain subject consent.
2. Obtain subject's new screening identification (ID) assigned by interactive response technology (IRT)
3. Determine subject eligibility through inclusion/exclusion criteria.
4. Record demographic information and prior trial identifiers (screening ID, subject ID, site ID, prior tolvaptan ADPKD trial protocol number).
5. Record medical/ADPKD history using prior trial data.
6. Review dietary recommendations and compliance
7. Record vital signs (post-void weight and seated heart rate) and in-clinic calibrated blood pressure (BP) measurement. Record height.
8. Collect blood for serum chemistry, liver function panel (ALT, AST, BT, bilirubin [direct], and alkaline phosphatase), serum sodium, serum creatinine, and hematology and coagulation. Hepatitis testing is optional. If hepatitis testing is performed, then both pre- and post-counseling activities relating to hepatitis testing are to be carried out based on local requirements and best practices.
9. Collect urine for urinalysis, urine osmolality (optional), and urine specific gravity.
10. Perform urine pregnancy test on women of childbearing potential (WOCBP). If positive, a follow-up serum test will be performed.
11. Conduct full physical examination.
12. Enter subject into IRT including prior trial identifier/information (protocol number, subject ID), confirmed dose regimen, and scheduled date of next visit.
13. Assess AEs reported as ongoing or resolved from prior trial to determine entry as medical history or ongoing event for this trial.
14. Record ongoing concomitant medications. (This will happen only if the screening visit occurs simultaneously with the last visit from a previous tolvaptan trial).

Protocol 156-13-211

3.7.1.2 Baseline (Day 0)

The baseline visit is the beginning of the treatment period in this trial. At the baseline visit, subjects will retain the subject number assigned in the previous tolvaptan trial, and the following assessments and procedures will be performed:

1. Review inclusion/exclusion criteria.
2. Review dietary recommendations and compliance.
3. CCI [REDACTED]
4. Record vital signs (post-void weight, seated heart rate, and calibrated blood pressure measurement).
5. Dispense at-home urine pregnancy test kits to WOCBP to be used if a menstrual period is missed before the next visit.
6. An optional directed physical examination may be performed to focus on PKD-related signs and symptoms.
7. Assess tolerability/dosing review of investigational medicinal product (IMP).
8. Enroll subject into trial through IRT and obtain IMP.
9. Dispense IMP (sufficient for 1 month or 3 months of dosing based on the subject's required visit schedule for hepatic evaluation as either monthly or every 3 months).
10. Provide subject with dosing instructions to begin on the following day.
11. Record ongoing concomitant medications
12. Assess AEs.

3.7.1.3 Monthly Visit (± 7 days)

The following subjects will return for a monthly visit to assess safety and tolerability of IMP and to monitor liver function.

- Subjects enrolling from the double-blind Trial 156-13-210 will have monthly trial visits/ALT level assessments for the first 18 months while treatment code from Trial 156-13-210 remains blinded, to ensure that they have adequate safety monitoring during this period of susceptibility. Once unblinding occurs, it can be determined which subjects received tolvaptan in Trial 156-13-210. These subjects may have their trial visits/hepatic transaminase monitoring change to every 3 months sooner as their previous tolvaptan exposure in Trial 156-13-210 can count towards the 18-month threshold. The investigator will need to discuss the change in frequency with the medical monitor before instituting the change.

Protocol 156-13-211

- Subjects from prior tolvaptan trials other than Trial 156-08-271 will have monthly trial visits/ALT level assessments for the first 18 months. After that, the trial visits/ALT monitoring will be conducted every 3 months after the change in frequency is confirmed with the medical monitor.
- Subjects enrolling from the open-label Trial 156-08-271 who have greater than 18 months of exposure to tolvaptan will have trial visits/ALT monitoring conducted every 3 months.

The following will be assessments will be completed:

1. Review dietary recommendations and compliance.
2. CCI [REDACTED]
3. Record vital signs (post-void weight, seated heart rate, and calibrated blood pressure measurement).
4. Collect blood for central laboratory assessments for serum sodium, serum creatinine, and ALT (see [Section 3.7.2.4](#)).
5. CCI [REDACTED]
6. CCI [REDACTED]
7. Urinalysis, urine osmolality (optional), urine specific gravity.
8. Perform urine pregnancy test on WOCBP (every 3 months). If positive, a follow-up serum test will be performed.
9. Dispense at-home urine pregnancy test kits to WOCBP, as required.
10. An optional directed physical examination may be performed to focus on PKD-related signs and symptoms.
11. Assess tolerability/dosing review of IMP.
12. Enter subject status in IRT, including any dose regimen changes and obtain IMP assignment.
13. Collect and reconcile returned IMP, assess compliance.
14. Dispense IMP based on subject's required visit schedule, and provide subject with dosing instructions.
15. Update concomitant medications.
16. Assess AEs.

3.7.1.4 Every 3 Months (± 14 days)

1. Review dietary recommendations and compliance.

Protocol 156-13-211

2. CCI [REDACTED]
3. Record vital signs (post-void weight, seated heart rate, and calibrated blood pressure measurement).
4. Collect blood for central laboratory assessments serum sodium, serum creatinine, ALT (see Section 3.7.2.4).
5. CCI [REDACTED]
[REDACTED]
6. Urinalysis, urine osmolality (optional), urine specific gravity.
7. Perform urine pregnancy test on WOCBP. If positive, a follow-up serum test will be performed.
8. Dispense at-home urine pregnancy test kits to WOCBP, as required.
9. CCI [REDACTED]
[REDACTED]
[REDACTED]
10. An optional directed physical examination may be performed to focus on PKD-related signs and symptoms.
11. Assess tolerability/dosing review of IMP.
12. Enter subject status in IRT, including any dose-regimen changes and obtain IMP assignment.
13. Collect and reconcile returned IMP; assess compliance.
14. Enter subject status in IRT, including any dose-regimen changes.
15. Dispense IMP based on subject's visit schedule, and provide subject with dosing instructions.
16. Update concomitant medications.
17. Assess AEs.

3.7.1.5 Early Termination/End of Treatment (+ 7 days)

At the early termination/end of treatment (EoTx) visit the following will be assessed:

1. Review dietary recommendations and compliance.
2. CCI [REDACTED]
3. Record vital signs (post-void weight, seated heart rate, and calibrated blood pressure measurement).
4. Collect blood for serum chemistry, serum creatinine, ALT, serum sodium and hematology and coagulation.

Protocol 156-13-211

5. CCI [REDACTED]
[REDACTED]
[REDACTED]
6. CCI [REDACTED]
7. Collect urine for urinalysis, urine osmolality (optional), urine specific gravity.
8. Perform urine pregnancy test on WOCBP. If positive, a follow-up serum test will be performed.
9. An optional directed physical examination may be performed to focus on PKD-related signs and symptoms.
10. Assess tolerability/dosing review of IMP.
11. Enter subject status in IRT, including any dose-regimen changes since the previous entry.
12. Collect and reconcile returned IMP; assess compliance.
13. Update concomitant medications.
14. Assess AEs.

3.7.1.6 7-day Follow-up Visit (+ 7 days)

1. Record vital signs (post-void weight, seated heart rate, and calibrated blood pressure measurement).
2. Collect blood for serum creatinine and ALT.
3. CCI [REDACTED]
[REDACTED]
[REDACTED]
4. Perform urine pregnancy test on WOCBP. If positive, a follow-up serum test will be performed.
5. Enter subject status in IRT.
6. Update concomitant medications.
7. Assess AEs.

3.7.2 Safety Assessments

3.7.2.1 Adverse Events

Refer to [Section 5, Reporting of Adverse Events](#).

Protocol 156-13-211

CCI [REDACTED]

CCI [REDACTED]

A list of the specific clinical laboratory assessments is presented in [Table 3.7.2.2-1](#).

Clinical laboratory samples will be collected and sent to the central laboratory at the following time points:

Screening: Hematology and coagulation panel, serum chemistry panel, liver function panel (AST, ALT, alkaline phosphatase, bilirubin direct [BT]) serum sodium, serum creatinine, urinalysis panel, urine osmolality (optional), urine specific gravity, urine pregnancy test (WOCBP) and hepatitis (optional).

Monthly visits (± 7 days): ALT (for the first 18 months for subjects enrolled from other tolvaptan ADPKD trials and Trial 156-13-210 while trial remains blinded), serum sodium, and serum creatinine (all subjects), urinalysis, urine osmolality (optional), urine specific gravity, and urine pregnancy test (every 3 months in WOCBP). CCI [REDACTED]

Every 3 months: (± 14 days): ALT (after 18 months of treatment for subjects enrolled from other ADPKD tolvaptan trials, or from Trial 156-13-210 after the trial is unblinded, and for subjects enrolled from Trial 156-08-271), serum sodium and serum creatinine, urinalysis panel, urine pregnancy test (WOCBP), urine osmolality (optional), and urine specific gravity. CCI [REDACTED]

Early Termination/EoTx (+ 7 days): Serum chemistry panel, hematology and coagulation panel, ALT, serum sodium and serum creatinine, CCI [REDACTED] urinalysis

Protocol 156-13-211

panel, urine pregnancy test (WOCBP), urine osmolality (optional), and urine specific gravity.

7-day Follow-up visit (+ 7 days): ALT, serum creatinine, and urine pregnancy test (WOCBP).

Table 3.7.2.2-1 Clinical Laboratory Assessments	

Hematology and Coagulation Panel: Hemoglobin Platelet count Mean corpuscular hemoglobin concentration (MCHC) Mean corpuscular volume (MCV) Red blood cell (RBC) count White blood cell (WBC) count with differential Prothrombin time (PT) as international normalized ratio (INR) Activated partial thromboplastin time (aPTT)
 
Urinalysis Panel: Appearance Color Blood Glucose Microscopic analysis, WBC/RBC counts per high power field pH Protein
 
Urine Chemistry Osmolality (optional) Specific gravity
 
Additional Tests: Urine (or serum) pregnancy for WOCBP Hepatitis (optional)
	
Serum Chemistry Panel: Albumin Blood urea nitrogen (BUN) Serum calcium Carbon dioxide Serum chloride Gamma-glutamyl transpeptidase Cholesterol, total Glucose Lactate dehydrogenase (LDH) Phosphorus Potassium Protein, total Uric acid
 
Liver Function Panel: Alkaline phosphatase (ALP) Alanine aminotransferase (ALT) Aspartate aminotransferase (AST) Bilirubin, total (BT) Bilirubin, direct

Creatinine	Sodium

If liver function panel, sodium and/or serum chemistry assessments are scheduled at the same visit, all values should be determined from the same blood sample. Blood testing for hepatitis will be optional for all subjects. Urine pregnancy testing will be performed with commercially available, high-sensitivity kits supplied to the subject by the site (acquired by the sponsor).

3.7.2.3 Physical Examination and Vital Signs

A full physical examination will be performed and documented at the screening visit although this may be combined with the last visit from the previous trial. At other visits,

Protocol 156-13-211

an optional directed physical examination may be performed to focus on ADPKD-related signs and symptoms. In some geographic regions, more frequent subject visits may be the norm; however vital signs and clinically significant physical findings will be recorded as an unscheduled visit in the electronic case report form (eCRF) as applicable. Any changes in medication or AEs will be recorded in the eCRF.

Height will be measured only at screening. Body weight will be taken post-void. It is preferable to use the same scale for each measurement. Clinic scales should be calibrated at least yearly. The investigator or his/her appointed designee is primarily responsible to perform the physical examination. If the appointed designee is to perform the physical examination, he/she must be permitted to do so by local regulations and his/her name must be included on any globally and locally required documents (eg, individual must be added for all sites on a US Food and Drug Administration (FDA) Form 1572, where local regulations allow, while local regulations determine their being named in the ICF). Whenever possible, the same individual should perform all physical examinations. Any undesirable condition present at a post-treatment physical examination that was not present at the baseline examination should be documented as an AE and followed to a satisfactory conclusion.

Vital sign data, including seated blood pressure, heart rate, height, and weight will be taken at the visits identified in the Schedule of Assessments ([Table 3.7-1](#)).

3.7.2.4 Assessment of Liver Symptoms, Signs or Test Abnormalities

Testing for hepatic transaminase (ALT/AST), alkaline phosphatase, bilirubin direct, and BT will be performed during screening. Subjects enrolling from the double-blind Trial 156-13-210 will have monthly ALT assessments for the first 18 months while the treatment code from Trial 156-13-210 remains blinded to ensure that all subjects have adequate safety monitoring during this period of susceptibility. Once unblinding occurs, it can be determined which subjects received tolvaptan in Trial 156-13-210. These subjects may have their trial visits/hepatic transaminase monitoring changed to every 3 months sooner as their previous tolvaptan exposure in Trial 156-13-210 can count towards the 18-month threshold.

Following the first 18 months, ALT assessments will be made every 3 months for Trial 156-13-210 subjects and for subjects from other tolvaptan ADPKD trials besides Trial 156-08-271.

Subjects enrolling from the open-label Trial 156-08-271 who have tolvaptan exposure greater than 18 months will continue with ALT monitoring every 3 months.

Protocol 156-13-211

Subjects enrolling from prior tolvaptan trials besides Trial 156-08-271 will have monthly ALT assessments for the first 18 months. Upon reaching 18 months of exposure and after confirmation from the medical monitor, the frequency of ALT monitoring for these subjects will occur every 3 months.

ALT will also be assessed at the Early Termination/EoTx visit and at the 7-day Follow-up visit.

Management of liver abnormalities is discussed in the paragraphs below.

3.7.2.4.1 Liver Test Abnormalities and Interruption/Discontinuation of Investigational Medicinal Product

An ALT elevation $2 \times$ ULN or the appearance of any suspicious symptom or sign should trigger prompt testing of hepatic function (ie, within 72 hours). Local laboratory testing is acceptable, ideally with a concurrent central laboratory sample for confirmation.

Any transaminase or bilirubin values which exceed $2 \times$ ULN should also prompt immediate retesting within 72 hours. While values remain in an abnormal range, testing frequency should be increased to at least weekly for the first month, gradually returning to monthly, or every three months as indicated by the results.

Liver transaminase levels reaching or exceeding $2 \times$ ULN that have an uncertain or rapidly increasing trajectory should prompt at least temporary IMP interruption. Tolvaptan should not be resumed until monitoring indicates abnormalities have resolved, are stable, or are not rapidly increasing, and then only with an increased frequency of monitoring.

Subjects would not typically be allowed to resume treatment with tolvaptan if they have:

- transaminase levels rise above $8 \times$ ULN,
- transaminase levels are $> 5 \times$ ULN for more than 2 weeks, or
- concurrent elevations of transaminase $> 3 \times$ ULN and BT $> 2 \times$ ULN.

Subjects with these levels of abnormality may be re-challenged with IMP if abnormalities were adjudicated as having a $< 50\%$ likelihood of being related to IMP (per DILI network [DILIN] probability criteria)¹⁰ by an independent hepatic adjudication committee (HAC) and the investigator and medical monitor agree to an intensive monitoring plan to mitigate risk. The subject must also be willing to comply with these monitoring measures, be informed of the potential risks, and consent to IMP re-challenge.

Protocol 156-13-211

3.7.2.4.2 Requirements for Special Reporting Using the Liver Disease Electronic Case Report Form and Immediately Reportable Event Form

The purpose of the liver disease eCRF and optional additional testing is to facilitate review of each subject who presents with, or develops a liver abnormality during the trial and to determine the probable cause(s) of these abnormalities. The review will be performed by a blinded, independent, HAC using DILIN probability criteria (< 25% = unlikely, 25% to 50% = possibly, 51% to 75% = probably, 76% to 95% = very likely, > 95% = definite).¹⁰ The result of these analyses may be presented separately from the CSR.

The investigator must complete a special liver disease eCRF for any subject who:

1. Discontinues treatment due to a liver-related AE,
2. Reports a serious liver-related AE,
3. Has normal screening levels and develops ALT or AST levels $\geq 3x$ ULN,
4. Has normal screening levels and develops BT levels $\geq 2x$ ULN, or
5. Has an abnormal screening level and develops abnormalities in that test that are > 2x the upper limit of their highest screening value.

CCI [Redacted]

[Redacted] Additional clinical testing (such as testing for hepatitis serology) may also be indicated and their results reported according to local guidelines. The liver eCRF and Immediately Reportable Event (IRE) form (see [Section 5.3](#)) should be updated as new information becomes available.

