^eCentral laboratory non-fasting serum laboratory tests will be performed. All subjects must be monitored for hepatic safety monthly until they have known tolvaptan exposure data of at least 18 months. After that, and following the approval of the medical monitor, hepatic monitoring will take place every 3 months. Trial 156-13-210 subjects who are eligible for this trial will have trial visits/hepatic monitoring monthly for the first 18 months of this trial then every 3 months thereafter, because their tolvaptan exposure will be unknown. Once unblinding occurs, it can be determined which subjects received tolvaptan in Trial 156-13-210. These subjects may have their trial visits/hepatic transaminase monitoring changed to every 3 months sooner as their previous tolvaptan exposure in Trial 156-13-210 can count towards the 18 month threshold. Subjects who enroll from other ADPKD tolvaptan trials will be monitored for hepatic safely monthly for their first 18 months they are in this trial.

^fHepatitis testing at screening will be optional. If hepatitis testing is performed, then both pre- and post-counseling activities relating to hepatitis testing are to be carried out based on local requirements and best practices. Upon request, if clinically indicated and approved by the medical monitor, subjects may have the following evaluations in addition to the protocol-specified chemistry panel: serum calcium, phosphorous, parathyroid hormone, vitamin D, and bicarbonate levels.

^gA full liver function panel (AST, ALT, alkaline phosphatase, BT) will be done at screening. All other liver function tests at subsequent visits are for ALT only, unless otherwise clinically indicated. An ALT elevation > 2 × ULN should trigger prompt testing of hepatic function within 72 hours. Any transaminase or bilirubin values which exceed 2 × ULN should prompt immediate retesting within 72 hours. While values remain in an abnormal range, testing frequency should be increased to at least weekly for the first month, gradually returning to monthly, and every 3 months as indicated by the results. Local liver function panel analyses will also be performed more frequently, if necessary.

^hUrine osmolality is optional.

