Liver transaminase or bilirubin levels reaching or exceeding $2 \times$ ULN that have an uncertain or rapidly increasing trajectory should prompt at least temporary IMP interruption. Tolvaptan should not be resumed until monitoring indicates abnormalities have resolved, are stable, or are not rapidly increasing, and then only with an increased frequency of monitoring.

Subjects would not typically be allowed to resume treatment with tolvaptan if they have:

- transaminase levels rise above $8 \times$ ULN,
- transaminase levels are $> 5 \times$ ULN for more than 2 weeks, or
- concurrent elevations of transaminase $> 3 \times$ ULN and BT $> 2 \times$ ULN.

Subjects with these levels of abnormality may be re-challenged with IMP if abnormalities were adjudicated as having a $< 50\%$ likelihood of being related to IMP (per DILI network

Protocol 156-13-211

[DILIN] probability criteria)¹⁰ by an independent hepatic adjudication committee (HAC) and the investigator and medical monitor agree to an intensive monitoring plan to mitigate risk. The subject must also be willing to comply with these monitoring measures, be informed of the potential risks, and consent to IMP re-challenge.

3.7.2.4.2 Requirements for Special Reporting Using the Liver Disease Electronic Case Report Form and Immediately Reportable Event Form

The purpose of the liver disease eCRF and optional additional testing is to facilitate review of each subject who presents with, or develops a liver abnormality during the trial and to determine the probable cause(s) of these abnormalities. The review will be performed by a blinded, independent, HAC using DILIN probability criteria (< 25% = unlikely, 25% to 50% = possibly, 51% to 75% = probably, 76% to 95% = very likely, > 95% = definite).¹⁰ The result of these analyses may be presented separately from the CSR.

The investigator must complete a special liver disease eCRF for any subject who:

1. Discontinues treatment due to a liver-related AE,
2. Reports a serious liver-related AE,
3. Has normal screening levels and develops ALT or AST levels $\geq 3x$ ULN,
4. Has normal screening levels and develops BT levels $\geq 2x$ ULN, or
5. Has an abnormal screening level and develops abnormalities in that test that are > 2x the upper limit of their highest screening value.

CCI [REDACTED]
[REDACTED]

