^eCentral laboratory non-fasting serum laboratory tests will be performed. All subjects must be monitored for hepatic safety monthly until they have known tolvaptan exposure data of at least 18 months. After that, and following the approval of the medical monitor, hepatic monitoring will take place every 3 months. Trial 156-13-210 subjects who are eligible for this trial will have trial visits/hepatic monitoring monthly for the first 18 months of this trial then every 3 months thereafter, because their tolvaptan exposure will be unknown. Once unblinding occurs, it can be determined which subjects received tolvaptan in Trial 156-13-210. These subjects may have their trial visits/hepatic transaminase monitoring changed to every 3 months sooner as their previous tolvaptan exposure in Trial 156-13-210 can count towards the 18 month threshold. Subjects who enroll from other ADPKD tolvaptan trials will be monitored for hepatic safety monthly for their first 18 months they are in this trial.

^fHepatitis testing at screening will be optional. If hepatitis testing is performed, then both pre- and post-counseling activities relating to hepatitis testing are to be carried out based on local requirements and best practices. Upon request, if clinically indicated and approved by the medical monitor, subjects may have the following evaluations in addition to the protocol-specified chemistry panel: serum calcium, phosphorous, parathyroid hormone, vitamin D, and bicarbonate levels.

^gA full liver function panel (AST, ALT, alkaline phosphatase, BT) will be done at screening. All other liver function tests at subsequent visits are for ALT only, unless otherwise clinically indicated. An ALT elevation > 2 × ULN should trigger prompt testing of hepatic function within 72 hours. Any transaminase values which exceed 2 × ULN should prompt immediate retesting within 72 hours. While values remain in an abnormal range, testing frequency should be increased to at least weekly for the first month, gradually returning to monthly, and every 3 months as indicated by the results. Local liver function panel analyses will also be performed more frequently, if necessary.

^hUrine osmolality is optional.

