Section 5.3, Immediately Reportable Events	The investigator must immediately report within 24 hours after either the investigator or site personnel become aware of any SAE, an AE that necessitates IMP discontinuation, any new liver result meeting the AE laboratory threshold criteria, any AE of special interest or a confirmed pregnancy , by telephone or by fax to the sponsor as outlined in Appendix 1. An IRE form must be completed and sent by fax, email or overnight courier to the sponsor. (Please note that the IRE form is NOT the AE eCRF).	The investigator must immediately report within 24 hours after either the investigator or site personnel become aware of any SAE, new liver laboratory abnormality requiring special liver eCRF completion, or confirmed pregnancy , by telephone or by fax to the sponsor as outlined in Appendix 1. An IRE form must be completed and sent by fax, email, or overnight courier to the sponsor. (Please note that the IRE form is NOT the AE eCRF).
Appendix 5, Title change	Protocol Amendment	Protocol Amendments and Administrative Changes

ADDITIONAL RISK TO THE SUBJECT:

There is no additional risk to the subjects.

Protocol 156-13-211

Amendment Number: 2

Issue Date: 25 February 2015

PURPOSE:

The primary purpose of this amendment was to add additional language at the request of the United Kingdom (UK)’s Medicines and Healthcare products Regulatory Agency (MHRA) and to correct the footnote in the Schedule of Assessments table to be consistent with protocol text.

BACKGROUND:

The UK MHRA wanted a more clearly defined end of trial date and more detailed language regarding abstinence as a birth control method.

Sectional Revisions

Location	Old Text	Updated Text

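### The UK protocol omits bilirubin from the drug-interruption rule and the schedule-footnote retest trigger, although its own body retest rule and the global protocol include it

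*Protocol*

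**What the plan says.** The Protocol file holds two texts dated 06 March 2015 for the same trial: a global version (Amendment 2) and a UK version (Amendment 3, UK). Each contains three matching instructions on liver values around 2 × ULN.

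- **Body retest rule, Section 3.7.2.4.1.** Both versions begin "Any transaminase or bilirubin values which exceed" 2 × ULN and call for a repeat within 72 hours.
- **Table 3.7-1, footnote g.** Global: "Any transaminase or bilirubin values which exceed 2 × ULN should prompt immediate retesting within 72 hours". UK: "Any transaminase values which exceed 2 × ULN should prompt immediate retesting within 72 hours".
- **Interruption rule, Section 3.7.2.4.1.** Global: "Liver transaminase or bilirubin levels reaching or exceeding" 2 × ULN. UK: "Liver transaminase levels reaching or exceeding" 2 × ULN. Both continue "that have an uncertain or rapidly increasing trajectory should prompt at least temporary IMP interruption".

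On routine testing after screening, footnote g says "All other liver function tests at subsequent visits are for ALT only, unless otherwise clinically indicated". UK Amendment 2 gives one of its purposes as to "correct the footnote in the Schedule of Assessments table to be consistent with protocol text".

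The UK text does use bilirubin elsewhere. In Section 3.7.2.4.1, total bilirubin above 2 × ULN together with transaminase above 3 × ULN normally bars resumption. In Section 3.7.2.4.2, total bilirubin of at least 2 × ULN after normal screening levels requires the special liver eCRF, and Section 5.3 makes such an abnormality reportable within 24 hours.

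**The concern.** There are two separate faults.

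The first is a missing safety trigger. Under the global text, a bilirubin of at least 2 × ULN with an unclear or rapidly rising course should lead to at least a temporary stop. Under the UK text the same value has to be retested, entered on the liver eCRF if screening was normal, and reported within a day, but no written rule links it to stopping drug.

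The second is a contradiction within the UK text. The body demands a bilirubin retest and the schedule footnote leaves it out. A site working from the schedule could miss it.

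Section 1.3 describes idiosyncratic hepatic toxicity as the most notable safety issue of chronic use. Section 2.1 cites 3 subjects who reached combined transaminase and bilirubin criteria and an estimated 1:4,000 risk of irreversible injury without adequate monitoring and management. It names interruption or discontinuation among the interventions meant to reduce that risk. A regional gap in the interruption rule therefore falls on the hazard that the monitoring exists to control.

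**Working it through.** No sample size, power or event figure is involved; the check is a comparison of text.

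**Step 1. Which statements name bilirubin?**

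| Instruction | Global text | UK text |
|---|---|---|
| Body retest rule, 3.7.2.4.1 | yes | yes |
| Footnote g retest trigger, Table 3.7-1 | yes | no |
| Interruption rule, 3.7.2.4.1 | yes | no |
| Total | 3 of 3 | 1 of 3 |

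The 2 × ULN level is the same in both versions; only the analytes differ. All six are complete sentences in current text, so neither redaction nor a broken table explains the difference.

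**Step 2. Does the amendment history explain it?** UK Amendment 2 describes the footnote edit as aligning it with protocol text. The body sentence that matches the edited one is the retest rule, and that still names bilirubin. The regulator's requests given as background to the amendment concern the end-of-trial date and abstinence as contraception. No reason is given for treating bilirubin differently in the UK. If the omission was intended, the UK body retest rule is wrong; if it was not, the footnote and the interruption rule are wrong. Either way the UK text needs correcting.

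**Step 3. Who falls into the gap?**

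- *Isolated bilirubin of at least 2 × ULN, rising fast or unclear:* interruption under the global rule, no written trigger in the UK.
- *ALT stable between 2 and 3 × ULN, or falling, with bilirubin climbing past 2 × ULN:* the transaminase course does not meet the UK interruption rule. The not-to-resume criterion needs transaminase above 3 × ULN, and it governs resumption rather than stopping. Again there is no UK trigger.
- *Bilirubin of at least 2 × ULN with a clearly stable course:* no interruption trigger in either version.
- *Transaminase of at least 2 × ULN with a qualifying course:* interruption in both versions, whatever the bilirubin.

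**Step 4. How often would it arise?** Footnote g schedules total bilirubin once per subject, at screening. Later values come from testing prompted by ALT at 2 × ULN, by a suspicious symptom or sign, or by other clinical need. The numbers should be small, but those later values will come mainly from subjects already under suspicion of liver injury. The documents do not give the number of UK subjects, so no count can be derived.

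**Step 5. Does any analysis change?** No. The dechallenge and time-to-offset summaries in Protocol Section 3.5.1 and SAP Section 8 concern transaminase elevations only.

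**The case against.** The strongest reply is that the UK text already protects these subjects by other means.

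- The body retest rule covers bilirubin, and the UK visit instructions send sites to Section 3.7.2.4 when ALT is drawn. A narrower footnote does not cancel the body rule. This stands to the extent that the retest half is mainly an inconsistency. Sites still hold two conflicting instructions.
- Section 3.7.5 lists liver test abnormalities, without limiting them to transaminases, among reasons to interrupt drug, and requires medical monitor approval before resumption. Section 3.8.3 requires withdrawal for a laboratory abnormality that the investigator judges to warrant it. These are general powers with no threshold, so they do not replace the specific rule.
- On the ALT-prompted route, the transaminase is already near 2 × ULN and may itself qualify. It may, but not when ALT is stable or falling while bilirubin climbs.
- The global rule also leaves the investigator to judge the trajectory. True: the contrast is between explicit guidance on bilirubin and general authority, not between an automatic stop and none.
- The denominator of three is a choice. Adding the not-to-resume criterion and the liver eCRF criterion, which name bilirubin in both versions, gives 3 of 5 for the UK against 5 of 5 globally. The same two statements differ under either count, and neither count measures risk.
- The hepatic adjudication committee reviews liver eCRF cases and its results reach the IDMC at least quarterly. That review does not tell the site whether to stop drug at the time.

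**Conclusion.** The point holds. Of three matching liver-action statements, the UK text names bilirubin in one and the global text in all three. The consequence is a missing written interruption trigger for UK subjects whose bilirubin is rising or of unclear course without a qualifying transaminase rise, plus a contradiction within the UK protocol on retesting. The reach is narrow: bilirubin is scheduled once, a stable bilirubin is treated alike in both versions, the not-to-resume criterion is the same, and no table or listing is affected. The expectation of few affected subjects rests on the testing schedule, not on a count. It should still be corrected, because it concerns subject safety for the drug's main known risk and the documents give no reason for the difference.

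**What to change.** Make two insertions in the UK protocol, using the sponsor's own global wording.

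1. Section 3.7.2.4.1, interruption rule: begin the sentence "Liver transaminase or bilirubin levels reaching or exceeding" 2 × ULN and leave the rest unchanged.
2. Table 3.7-1, footnote g: restore "Any transaminase or bilirubin values which exceed 2 × ULN should prompt immediate retesting within 72 hours".

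Both would then agree with the UK body retest rule and with the three global statements. The edit is two words in each place, with no effect on data collection, tables or listings. It cannot go through as an administrative change, since Section 13 reserves those for edits with no effect on subject safety or trial conduct. It needs a UK amendment, with ethics approval before implementation and submission to the regulator.
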